Appendix 1 – References		

# 1. BACKGROUND AND RATIONALE

Gout is a common inflammatory arthritis often seen in primary care. Worldwide prevalence ranges from under 1% to 6.8%. The prevalence of gout has risen over the past three decades, accompanied by an increase in morbidity.  In Singapore, prevalence of gout is 4.1% amongst the Singapore Chinese population. Gout is associated with significant morbidity and mortality due to coronary heart disease and kidney disease, and has substantial burden and impact in quality of life, with higher healthcare utilization and high unemployment rate observed in middle aged men with gout. 

Patients with poorly controlled gout suffer from frequent gout flares, with acute onset of joint pain and swelling, affecting health-related quality of life. A meta-synthesis showed that gout flares impact on patients' lives, including physical, psychological, social and family life. In a primary care institution in Singapore, 28.2% of patients with gout had poorly controlled disease. In a rheumatology clinic in Singapore, 33% of patients with gout visited emergency department at least once for gout flare, while 19.5% had at least one hospitalization for gout.

Acute gout flares can be mitigated by pharmacotherapy. Timely administration of acute medications is important to alleviate the pain leading to early resolution of symptoms. American College of Rheumatology (ACR) Guideline 2020^8 and European League Against Rheumatism (EULAR) 2016  recommend colchicine, non-steroidal anti-inflammatory drugs (NSAIDs) or corticosteroid for treatment of acute gout flare. In primary care clinics in Singapore, colchicine was often prescribed for an acute gout flare. However, colchicine has gastrointestinal side effects such as vomiting and diarrhoea, and some patients are not aware of its side effects and exceeded prescribed dose.  NSAIDs might improve the pain if given within 24 hours.  However, NSAIDs are associated with gastrointestinal, renal and cardiovascular adverse effects, thus they may not be the suitable pharmacotherapy for those with renal, gastrointestinal or cardiovascular comorbidities.  NSAIDs also cause hypersensitivity reactions with estimated prevalence of hypersensitivity to NSAIDs to be 0.5 to 1.9% of the general population.  For patients who are unable to tolerate NSAIDs or colchicine, or have chronic renal disease, systemic corticosteroid such as oral prednisolone might be a good alternative as it provides similar improvement in pain relief. 

Aside to pharmacotherapy, dietary control is important to prevent gout flares. ACG guideline 2020^8 includes conditional recommendations to reduce alcohol intake, adopt a low-purine diet, and prioritize weight loss. A meta-analysis showed that red meat, seafood, alcohol, fructose or sweetened soft drinks increase risk of gout and hyperuricaemia, while consumption of soy foods, dairy products and vegetables reduce risk of gout.  However, there is lack of awareness in dietary triggers especially in those with active gout.  A recent study in Australia found that patients with gout lack knowledge about the risk and protective factors of gout.  Patients resisted dietary changes due to the restrictive nature of the diet, lack of resources for information, and perceived it as unrealistic and unmanageable. 

Gout control remains suboptimal despite established guideline. Urate lowering therapy (ULT) remains the key in gout management and its initiation is recommended for patients with recurrent gout flares with treat-to-target strategy.  However, in primary care institution in Singapore, it was found that half of the patients with poorly controlled gout were not prescribed urate lowering therapy. In patients with gout, the overall adherence rate to ULT is as low as 47%. Patients with gout demonstrate poor adherence to urate lowering therapy as they have limited knowledge of gout and its treatment, their attitude and perception towards taking long term medications. Some patients avoid ULT due to fear of side effects or flares during initiation, leading to nonadherence. Self-management is important in the management of chronic diseases. Interventions of self-management have been shown to improve self-efficacy, health behavior, subsequently improving health status and quality of life

and reducing healthcare utilization.  Self-efficacy refers to an individual's belief in their capacity to execute behaviours necessary to produce specific performance attainments, and it is correlated with self-care. Raising self-efficacy is important to change behavior in self-care. 

An action plan is a patient-held guide to support self-management with educational value. In chronic diseases such as asthma, the action plan provides information on how to manage the disease on a day-to-day basis and has proven to encourage self-management, improve health outcomes and quality of life, and reduce unscheduled visits to physicians.  Likewise, gout is a chronic condition with acute gout flares intermittently, that will benefit from self-management. In a study in Malaysia, patients were capable in self-management of gout but to variable extent, some practice diet control, some use painkillers during acute gout attacks, some use traditional medicine rather than taking allopurinol, some use exercise or stress-reducing activities, and the type of self-management might be influenced by cultural and social factors. 

To our knowledge, there is no well recognised gout action plan. A gout action plan has not been subjected to prior development in terms of content, design and acceptability. We hope that by developing a gout action plan, it will give information to patients about the disease to raise knowledge on gout, to reduce frequency of exacerbation via dietary control and lifestyle measures, to provide information on pain relief medications and the risks of taking painkiller, and urate lowering therapy for those with recurrent gout flares, and safety-netting advice on when to seek help. The study thus aims to develop a prototype of gout action plan by incorporating patients' and primary care physicians' perspectives, hoping to improve quality of life and healthcare utilization among patients with gout.

# 2. HYPOTHESIS AND OBJECTIVES

Aims

Primary aims

- 1. Explore primary care professionals' (PCPs) perspectives and challenges in management of gout and assess whether novel gout action plan addresses the challenges.
- 2. Explore patients' understanding of gout, experiences and challenges of managing gout and medications, and assess whether they are willing to use novel gout action plan.

Secondary aims:

- 1. Assess the feasibility and acceptability of gout action plan in a pilot open label randomized controlled trial (RCT).
- 2. Assess preliminary effectiveness of gout action plan in reducing frequency of gout exacerbation, improving gout control and quality of life.

**Hypothesis** 

- 1. A prototype gout action plan can be developed to aid in management of gout.
- 2. In primary care professionals who manage patients with gout, there are variable views and perspectives towards gout action plan.
- 3. Patients have variable understanding and challenges of managing gout and different opinions in using gout action plan.
- 4. Gout action plan is an effective tool in reducing gout flares, improving gout control and quality of life.

# 3. EXPECTED RISKS AND BENEFITS

Expected risks

1. Data privacy

As this study involved audio-recording of the interview for transcribing of information and collection of basic demographic information using data collection form, there is a potential risk of data breach affecting participant's confidentiality.

2. Emotional risk

Emotional risk from an adverse emotional response to a sensitive topic breached during the interview process. The interviewer will explain to participants that they may refuse to answer any of the questions if they feel uncomfortable to answer the questions, may take a break at any time during the interview or choose to discontinue the study at any time.

3. Discomfort during blood taking

Patient might experience pain and minimal bleeding during the blood taking.

#### Benefits

Patients might benefit from the gout action plan and learn to self-manage gout in their daily life.

# 4. STUDY POPULATION

#### 4.1. List the number and nature of subjects to be enrolled.

The study will be conducted at Pasir Ris Polyclinic, one of the Singhealth Polyclinics. For first part of the study, due to its qualitative nature, we aim to recruit approximately 10-15 patients with gout and 10-15 healthcare professionals until data saturation is reached. For second part of the study on open label randomized controlled trial, we aim to recruit 72 participants.

Adult patients aged 21 and above with the clinical diagnosis of gout who are being followed up at Pasir Ris Polyclinic will be randomly recruited into the study. Healthcare professionals who involve in the care of gout will also be recruited into the first part of the study. Children or minorities will be excluded from the study.

#### 4.2. Criteria for Recruitment and Recruitment Process

#### Recruitment of patients:

Eligible patients will be identified through either screening from electronic medical records (EMR) using SingHealth Outpatient Appointment System (OAS) and Sunrise Clinical Manager (SCM) or referred by attending physicians to the study team. National Electronic Health Record (NEHR) will not be assessed for research purpose. The study team will obtain prior knowledge of a potential participant's medical appointment from the SingHealth OAS and SCM so that the physician can be reminded about the arrival of potential participant.

If potential patient participants show interest in the study, they will be directed to the study team. The study team will verify the eligibility, and after an initial explanation of the study, participant will be provided a copy of participant information sheet and consent forms to bring home and to think about their participation before the signing of the consent form on the day of interview or focus group discussion. Adequate time will be given to read the documents and questions, emphasizing the voluntary nature of participation and its independence from routine clinical care. Written informed consent will be obtained in-person at the study site, in a quiet and separate room or space, ensuring privacy. The study team member taking the consent will not be the treating physician of the patient. The participant will sign hard copies of the consent form, and the copies will be kept by participant and study team.

#### Recruitment of healthcare professionals:

Primary care healthcare professionals in Pasir Ris Polyclinic, and other clinics will be invited to participate in the in-depth interview. The study team will conduct a briefing about the study in clinic meeting and invite potential participants to take part. Potential participants who are not present at the clinic meeting will also be contacted by

study team in-person. The study team will ensure that there is no dependent or hierarchical relationship between the team and the potential HCP participants.

# 4.3. Inclusion Criteria

#### Inclusion Criteria

Inclusion Criteria (for patients):

- Adults who are 21 years old and above
- Clinical diagnosis of gout as per ACE-EULAR 2015 criteria
- Had at least an episode of gout exacerbation within the last 1 year
- Able to speak and read English
- Singapore citizens or permanent residents
- Able to provide informed consent

Inclusion Criteria (for healthcare professionals):

- Currently still in clinical practice
- Manage gout in their clinical practice

# 4.4. Exclusion Criteria

Exclusion Criteria

Exclusion Criteria (for patients)

- Mental disorders
- Cognitive impairment
- Hearing and/ or speech impairments
- Pregnant
- Known terminal illness
- Unable to provide informed consent

Exclusion Criteria (for healthcare professionals):

- Not involved in gout management in the practice
- No longer in clinical practice

# 5. STUDY DESIGN AND PROCEDURES/METHODOLOGY

The study will employ a sequential mixed-method design, which comprises of:

- 1. Qualitative research to develop and refine prototype of gout action plan by gathering perspectives from both patients and healthcare providers.
- 2. An open label pilot RCT to assess feasibility and acceptability of gout action plan, and preliminary outcome on effectiveness of gout action plan in reducing gout flares, improvement in uric acid and quality of life.

#### Part 1- Qualitative phase: Creation of a prototype gout action plan

Using written asthma action plan as a guide, a prototype gout action plan will be drafted based on the latest evidence. The gout action plan outlines how to manage gout, identifying triggers, recognizing when symptoms worsen, appropriate medication usage, and when to seek medical attention. It is categorized into zone system, which consists of green zone (well controlled), yellow zone (mild symptoms), red zone (severe symptoms).

**Qualitative phase**: In-depth interviews and focus group discussions will be conducted with primary care healthcare professionals (physicians, nurse, pharmacist, and dietician) who are involved in patient care, as well as patients with gout. The interviews and discussions will explore on their understanding of gout and its management, experiences of managing gout, perceptions of self-management, and opinions on the prototype of gout action plan. This will provide insights into iterative refinement of the gout action plan. Prototype will thus be refined down the multiple interactions of interview or discussions till data saturation is reached. For

healthcare professionals, maximum variation sampling will be employed based on their age and years of clinical experience. For patient, maximum variation sampling will be employed based on their age, ethnicity and socioeconomic status. The session will be audio-recorded.

#### Part 1A

In-depth interviews with patients and focus group discussions with patients will be conducted with patients with gout. The interviews and discussions will explore their understanding of disease and treatment, experience of patient-physician consult, perceptions of self-management, and opinions on prototype gout action plan. Interview guide is developed based on theoretical domain framework.

Basic patient demographics and data on their gout duration, comorbidities and medications will be collected using the attached data collection form.

Research questions to be explored with patients with gout:

- 1. To understand patients' knowledge, skills, and behaviours related to gout management.
- 2. To identify factors that influence adherence to treatment and lifestyle modifications.
- 3. To explore emotional, social, and environmental factors impacting gout management.
- 4. What is their experience of physician consultation for gout management?
- 5. What are their barriers and facilitators to gout self-management?

6. What is their opinion on the prototype gout action plan? Is it easily understandable? Is it informative enough? What are the barriers of using gout action plan? When will they use the gout action plan?

Topic guide is as attached in attachment section.

Subjects: primary care patients with gout exacerbation within 1 year

Sampling method: Convenience sampling. Maximum variation sampling will be employed based on their age, ethnicity and socioeconomic status.

Outcome: identification of themes, needs and information that will help in the creation of prototype gout action plan.

Expected participant participation time: 60 minutes

#### Part 1B

In-depth interviews with patients and focus group discussions with primary care providers, nurses, pharmacist, dietician. The interviews and discussion will explore their understanding of gout and experiences of managing gout, their views on self-management of gout, and views on gout action plan.

Research questions to be explored:

- 1. What is their understanding of gout and its management?
- 2. What are their experiences of treating gout patients? Do they know about treatment goals and urate-lowering therapy?
- 3. What is their perception about self-management?
- 4. What are their opinions on the prototype of gout action plan? What are the barriers and enablers of action plan? Do they think need any training or resources to support use of gout action plan?

Topic guide is as attached in attachment section.

Subjects: primary care healthcare professionals (physicians, nurses, pharmacist, dietician) who manage patients with gout

Sampling method: Convenience sampling and purposive sampling. Maximum variation sampling will be employed based on their age and years of clinical experience.

Outcome: identification of themes, needs and information that will help in the creation of prototype gout action plan.

Expected participant participation time: 60 minutes

The interviews and discussions will provide insights into iterative refinement of the gout action plan. Prototype will thus be refined down the multiple interactions of interview or discussions till data saturation is reached.

The session will be audio-recorded using audio recorder. After each interview, the interviewer will transfer the audio-recording to a password-protected corporate laptop and erase it from the audio-recorder. The audio recording will be transcribed verbatim using the research department's transcribing software or transcription platforms (such as transcribe.gov.sg or Note Buddy) or engagement of transcriptionist. All participant identifiers will be removed from the transcript to ensure confidentiality. All transcripts will be checked by interviewer for accuracy. De-identified data will be used for analysis. Analysis of data will be performed using a thematic approach. All the audio files and transcriptions of the recordings will have password encryption and stored in the same password-protected corporate laptop in workplace. Only study members will have access to the password. The electronic data will be kept for 6 years post completion of the study.

Participants who consented will be informed on the date and time of the in-depth interviews or focus group discussions. Participants who come for the in-depth interviews and focus group discussions will sign the written consent form before participation. After written consent is obtained, participants will be asked to fill up the data collection form which contains their basic demographics information and health status information. Participants will be de-identified. Participants will be briefed on the purpose of the study, their roles and rights. They will be informed that the interview or discussion will be audio recorded. Field notes will be taken to record non-verbal cues. Interviewer will use topic guide for the interview or discussion.

At the end of the interview or discussion, participant will be given token of appreciation.

#### Part 2: Open label pilot RCT

Quantitative phase – two-arm pilot randomized controlled trial (RCT)

- Arm 1: usual care + gout action plan for 24 weeks
- Arm 2: usual care

#### **Randomization**

Patients will be randomly assigned in a 1:1 ratio to either control or intervention arm in an open-label fashion, using computer-generated random numbers for randomization of subjects. The randomized sequence will be written and kept in an opaque sealed envelope and labelled with a serial number. When patients consent to participate in the study, the team will open the opaque sealed envelope and allocated them to the study arms accordingly. It is impossible to blind the patients and research team members to the patient allocation in view of the nature of the intervention.

Upon recruitment and after patient consented, basic patient demographics and data on their gout duration, comorbidities and medications will be collected using the attached data collection form. They will be asked to recall and self-report frequency of gout flares for the past 6 months prior to recruitment. They will also need to fill up an EQ-5D-5L questionnaire on health-related quality of life which takes approximately 5 minutes to fill it up. They will also be sent for laboratory for blood test to test for uric acid level. Blood will be taken from arm using a syringe and needle, during recruitment and at a 6-month visit, for participants in both intervention and control groups. About 3ml of blood will be taken each time. In total, there will be about 6ml taken over a period of 6 months. The Institutional Review Board waiver under Section 37(3) of the Human Biomedical Research Act

2015 ("HBRA") for the removal of human biological materials is not required. This is because we will collect samples from adults with mental capacity to personally give consent for this research study.

For those patients who are assigned into the intervention arm, they will be sent to care manager to explain on the gout action plan and its details.

Study participants will be followed up for 24 weeks after enrolment. At 24 weeks, they will be asked on their frequency on gout flares after the recruitment and to fill up the EQ-5D-5L questionnaire together. They will also be sent to laboratory for blood test on uric acid level. The follow up survey will be conducted by phone call or questionnaire at a convenient time for them or during the clinic visit.

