# 8. SAMPLE SIZE AND STATISTICAL METHODS

### 8.1. Determination of Sample Size

For qualitative part, sample size calculation is not applicable. Prototype of gout action plan will be refined until saturation is reached. Hennink  showed that 9-17 interviews or 4-8 focus group discussion reached saturation for studies with relatively homogenous study populations and narrowly defined objectives. Therefore, for this study, we aim to recruit 10-15 participants from each group.

For pilot RCT, based on sample size rule of thumb for pilot study, Browne  cites to 'use at least 30 subjects or greater to estimate a parameter', whereas Whitehead  suggests that pilot trial sample size to be 25 per treatment arm for small effect size of 0.2 for a main trial designed with 90% power and two-sided 5% significance. With a 6-months follow up visit, assuming a potential 30% attrition rate, the final sample size after buffering for drop out will be 36 per arm (n=72). The sampling method will be convenience sampling.

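### The stated allocation method names no restriction, so unless one is added the planned 36 per arm and the balance of baseline urate-lowering therapy are left to chance

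*Protocol*

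**What the plan says.** The Randomization text in Protocol section 5 (Part 2) gives the whole allocation method. "Patients will be randomly assigned in a 1:1 ratio to either control or intervention arm", "using computer-generated random numbers for randomization of subjects". The sequence is prepared in advance and concealed in opaque, sealed, serially numbered envelopes. After consent, "the team will open the opaque sealed envelope and allocated them to the study arms accordingly". The trial is open label: "It is impossible to blind the patients and research team members to the patient allocation". No block, stratum, minimisation factor or fixed-total list is mentioned.

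Section 8.1 cites two pilot rules of thumb: at least 30 subjects to estimate a parameter, and "pilot trial sample size to be 25 per treatment arm for small effect size of 0.2". After allowing for 30% attrition it concludes that "the final sample size after buffering for drop out will be 36 per arm (n=72").

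Section 1 presents urate-lowering therapy as central to gout management. It reports that, in a primary care institution in Singapore, "half of the patients with poorly controlled gout were not prescribed urate lowering therapy". Medications are recorded at recruitment. The regression in section 8.2 contains the intervention, the baseline value of the outcome, and demographic factors that reach p<0.1 in bivariate analysis.

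**The concern.** Section 8.1 plans a specific split, and the method in section 5 does not by itself deliver it. The planned figure has almost no slack, so most other splits leave the smaller arm with fewer than 25 expected completers.

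Baseline urate-lowering therapy bears directly on uric acid and flares, two of the outcomes of the pilot. It is collected at entry, but nothing in the allocation balances it. It is not a demographic factor in the ordinary sense, so the model in section 8.2 does not adjust for it. Baseline uric acid enters only the uric acid model.

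At stake is how readable the preliminary effect estimate will be with about 25 completers per arm. A visible therapy gap between arms would leave readers unsure what a difference in uric acid or flares reflects.

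**Working it through.** **Inputs.** From section 8.1: 25 per arm before attrition, 30% attrition, 36 per arm, 72 in total. From section 5: ratio 1:1. Assumption: the share of trial patients on urate-lowering therapy is not given. I take 50%, with a range of 30% to 70%. The only anchor is the section 1 figure for poorly controlled patients.

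**1. The plan's own figure.** 25 / (1 − 0.30) = 35.7, rounded up to 36 per arm and 72 in total. This agrees with section 8.1.

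**2. Arm sizes if allocation is unrestricted.** The size of one arm is Binomial(72, 0.5).

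| Event | Probability |
|---|---|
| exactly 36:36 | 9.4% |
| 37:35 or better | 27.6% |
| 40:32 or worse, 2·P(X ≤ 32) | 41.0% |
| 44:28 or worse, 2·P(X ≤ 28) | 7.6% |

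The expected size of the smaller arm is 32.6.

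**3. Consequence for completers.** Expected completers are 0.70 × arm size: 25.2 from 36 patients, 24.5 from 35, 22.4 from 32 and 19.6 from 28. If each patient completes independently with probability 0.70, both arms reach 25 completers with probability 37.1% under a fixed 36:36 and 23.2% under unrestricted allocation.

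**4. Consequence for precision.** Relative efficiency is 4·n1·n2 / 72².
- 40:32 gives 4·40·32 / 5184 = 0.988, a loss of about 1%.
- 44:28 gives 4·44·28 / 5184 = 0.951, a loss of about 5%.

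**5. Therapy balance if allocation is unrestricted.** Users and non-users are each allocated with probability 0.5, and all splits are enumerated.

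| Users among 72 | gap ≥ 15 points | gap ≥ 20 points |
|---|---|---|
| 36 (50%) | 19.6% | 8.4% |
| 22 or 50 (about 30% or 70%) | 16.2% | 7.1% |

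Letting the number of users vary at random gives 20.4% and 8.9% at 50% use, and 17.0% and 6.7% at 30% or 70%. Fixing the arms at 36:36 without stratifying barely helps: a gap of 20 points or more still occurs in 7.6% of lists at 50% use. Arm size and therapy balance therefore need separate remedies.

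**6. The proposed scheme.** I simulated blocks of 4 or 6 chosen at random within two therapy strata, with 30%, 50% and 70% use. The block sizes are illustrative. Exactly 36:36 occurs in about 55% of lists and 37:35 or better in about 98%. The largest therapy gap seen was about 8 points.

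**The case against.** The strongest reply is that the protocol never says simple randomisation. A computer-generated list permuted to 36:36, or a blocked list, would fit its words, and block details are often kept out of an open-label protocol to protect concealment. This stands as a condition: the figures in steps 2 to 5 apply only if the list is run unrestricted. It does not remove the point, because the restriction has to be settled before the first envelope is opened and the only method stated does not secure the split.

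Second, chance imbalance does not bias a randomised comparison, the efficiency loss is small, and this is a pilot. All of that is correct and limits the weight of the point. Adjustment for the baseline outcome will also carry part of the prognostic effect of therapy.

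Third, the proposed scheme does not always give 36:36. That is also correct. It trades exact equality for therapy balance.

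A reader might also infer three stronger things that the protocol does not support:
- **That exactly 36 per arm is required.** Section 8.1 uses rules of thumb and a guessed attrition rate, with no power requirement for the pilot. Even a perfect 36:36 reaches 25 completers in both arms only 37% of the time, so attrition is the larger source of shortfall.
- **That 25 per arm is the only basis for the size.** The 30-subject rule is cited beside it, although the 36 is reproduced from the 25.
- **That the whole sequence sits in one envelope.** The text reads "The randomized sequence will be written and kept in an opaque sealed envelope and labelled with a serial number". The singular is loose wording. The serial number, and the opening of an envelope as each patient consents, point to one numbered envelope per patient.

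**Conclusion.** The point holds as a modest improvement to the design. The protocol states no restriction on allocation. If none is applied, 36:36 arises in 9.4% of lists and 40:32 or worse in 41%. Baseline therapy then differs by 20 points or more in about 8% of lists at 50% use, or about 7% at 30% or 70%, with no stratification to prevent it and no named covariate to correct for it.

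The conclusion rests on two assumptions: that the absence of any stated restriction means unrestricted allocation, and that therapy use lies between 30% and 70%. If the investigators already intend a fixed or blocked list, one sentence settles the arm-size part. The therapy part would remain. The comparison is unbiased either way, and the pilot is not invalidated.

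**What to change.** **Section 5, Randomization.** State that allocation uses permuted blocks of randomly varying size, stratified by urate-lowering therapy at baseline (yes/no), with therapy status recorded before the envelope is opened. Keep the block sizes undisclosed to the recruiting team, in a separate randomisation document.

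**Section 8.2, Quantitative data.** Pre-specify baseline urate-lowering therapy as a covariate in each outcome model, whatever its p-value. Use the status at baseline only, since later changes could be a result of the intervention.

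**Cost.** Two changes of protocol wording, a different list and a separate envelope series for each stratum, all before the first allocation. No extra patients, visits or staff are needed, because medications are already recorded at recruitment. The covariate uses one degree of freedom per model. The downside is slight predictability at block ends in an open-label trial, which varying and undisclosed block sizes limit.

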# 7. DATA ANALYSIS

#### 7.1. Data Quality Assurance

Study data will be checked and validated by data management executive in Department of Research to ensure that the data obtained from this research is accurate, complete and reliable.

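### The statement that no research team member can be masked is broader than its reason allows, and leaves the 24-week flare count and EQ-5D-5L open to avoidable interviewer influence

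*Protocol*

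**What the plan says.** All of the relevant text is in protocol section 5, Part 2, under Randomization, unless another section is named.

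- **Design:** "Patients will be randomly assigned in a 1:1 ratio to either control or intervention arm in an open-label fashion".
- **Masking:** "It is impossible to blind the patients and research team members to the patient allocation", with the nature of the intervention given as the reason. No role within the team is excepted.
- **Who learns the arm:** once a patient consents, "the team will open the opaque sealed envelope and allocated them to the study arms accordingly". Intervention patients then see one further person: "they will be sent to care manager to explain on the gout action plan and its details".
- **Outcomes at 24 weeks:** "they will be asked on their frequency on gout flares after the recruitment and to fill up the EQ-5D-5L questionnaire together". Patients also have blood taken for uric acid, which the same section places at recruitment and at a 6-month visit in both arms.
- **Mode of collection:** "The follow up survey will be conducted by phone call or questionnaire at a convenient time for them or during the clinic visit". The person who does this is not named.
- **Baseline:** patients fill in the EQ-5D-5L themselves at recruitment and report their flares over the preceding 6 months from memory.
- **Data handling:** section 7.1 says "Study data will be checked and validated by data management executive in Department of Research", and section 10 has the study team review the collected data each month. Section 8.2 lists the between-arm tests but not who runs them.

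**The concern.** The reason given does not support so wide a statement. A plan that patients hold, and that a care manager explains to one arm only, cannot be hidden from those patients or from that care manager. It does not follow that a different person who telephones at 24 weeks must know the arm. By declaring masking impossible for the team as a whole, the protocol closes off protection that it could have had.

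This matters because two of the three effectiveness outcomes, flares and quality of life, rest on patient report. A flare count recalled over about six months depends on how the question is put, whether the patient is prompted, and what is accepted as a flare. A caller who knows the arm can affect all of these without intending to. The choice of mode is left to convenience, so a patient who completed the EQ-5D-5L in writing at baseline may answer it by phone at 24 weeks, and nothing requires the mode to be recorded. Any influence of this kind would enter the preliminary effectiveness estimates and could not be removed afterwards.

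**Working it through.** **Step 1. Test the reason against each role.**

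| Role | Does the intervention itself reveal the arm? | Covered by the protocol's statement? |
|---|---|---|
| Patient | Yes: holds the plan or does not | Yes |
| Care manager | Yes: sees intervention patients to explain the plan | Yes |
| Team member who opens the envelope | Knows the arm from allocation, not from the intervention | Yes |
| Person who takes the 24-week survey | No, unless also in one of the roles above or told by the patient | Yes |

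The reason supports the first two rows. The third row is unmasked by the task itself. The fourth row is a matter of assigning roles.

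**Step 2. Exposure of each 24-week outcome.**

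| Outcome | Source | Exposure to interviewer influence |
|---|---|---|
| Flare frequency | Patient recall, asked | Yes, if asked by a person who knows the arm |
| EQ-5D-5L | Patient report, by phone, questionnaire or at the visit | Yes by phone; little if self-completed |
| Uric acid | Laboratory | Little |

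**Step 3. Reproduce the plan's own figure.** Section 8.1 takes 25 per arm from a rule of thumb and allows for 30% attrition: 25 / (1 − 0.30) = 35.7, rounded up to 36 per arm and 72 in total. This agrees with the protocol. Expected completers are 36 × 0.70 = 25.2, about 25 per arm. The masking point does not depend on this figure.

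**Step 4. Illustration of size.** The protocol gives no value for interviewer-induced bias. Suppose there is no true effect, and suppose a pure shift of b standard deviations between arms in a continuous outcome. The 0.05 threshold comes from section 8.2; two-sided testing of the pilot's own comparisons and the normal approximation are assumptions. Then

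- SE of the standardised difference = √(2/n): √(2/25) = 0.283 and √(2/36) = 0.236.
- False-positive rate = 1 − Φ(1.96 − b/SE) + Φ(−1.96 − b/SE).

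| Assumed b (SD) | 25 completers per arm | 36 per arm |
|---|---|---|
| 0 | 5.0% | 5.0% |
| 0.1 | 6.4% | 7.1% |
| 0.2 | 10.9% | 13.6% |
| 0.3 | 18.6% | 24.7% |
| 0.5 | 42.4% | 56.4% |

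The table shows only what a given shift would do. It is not evidence that any of these shifts would occur.

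**The case against.** The strongest reply is that the trial is openly unmasked and is a pilot. Its trial aims are feasibility, acceptability and only preliminary effectiveness. Patients know their arm, so their own reporting bias remains whoever collects the answers, and they may reveal the arm during a call. All of this stands, and it limits the weight of the point. It does not make the impossibility statement correct, and it does not justify leaving in place the part of the bias that can be avoided.

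It can also be said that the protocol does not state that unmasked staff will phone patients. That is right: the collector is unnamed, phone is one of several options, self-completion is already allowed, and the word together in the EQ-5D-5L sentence may mean only alongside the flare question. The fair reading is that collection by a person who knows the arm is not excluded. Likewise, a change of mode arises only if phone is used. The same options are open to both arms, and the protocol gives no reason to expect different use between them.

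A reader might go further and infer that the analysis is unmasked too, or that an analyst who knows the arm would be choosing covariates and cut-points. The protocol does not support this. Section 8.2 names no quantitative analyst and does not mention analyst masking, which may be set in an analysis plan that is not shown. Covariates follow a stated rule (baseline outcome, plus demographic factors with p below 0.1), which gives the same result with coded or named arms. The absence of cut-points would be a matter of specification, not of masking.

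A reader might also set an assumed shift against the effect size of 0.2 in section 8.1. That figure belongs to the future main trial in a pilot-size rule of thumb. It is not an effect that this pilot is sized to detect, so the comparison says little.

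**Conclusion.** The point holds in a limited form. The statement that the whole team cannot be masked exceeds the reason given for it. As a result, the protocol offers no protection against interviewer influence on the two patient-reported 24-week outcomes and does not fix how the EQ-5D-5L is administered relative to baseline.

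The size of any bias cannot be derived from the protocol. If it were 0.1 to 0.2 SD, which is an assumption without support in the document, the false-positive rate at 25 completers per arm would be 6.4% to 10.9% instead of 5%. Larger shifts would do more, but nothing in the protocol points to them. Uric acid is little affected, and bias from patients who know their arm would remain after any change. The practical effect is therefore modest. The change is still worth making because it is cheap before enrolment and cannot be made retrospectively.

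**What to change.** 1. In the Randomization text, limit the impossibility statement to patients and the care manager who explains the plan.
2. Make patient self-completion of the flare question and the EQ-5D-5L at the existing 6-month blood-test visit the default in both arms. This removes most interviewer influence and keeps the EQ-5D-5L mode the same as at baseline.
3. Allow phone only as a fallback, with a fixed script identical in both arms. Where feasible, the caller should be an existing team member who took no part in that patient's allocation or in delivering the plan. This lowers the chance that the caller knows the arm but does not guarantee masking, since the study team reviews data monthly and patients may disclose their arm.
4. Record the mode of collection for every patient.
5. Optionally, have the data management executive supply the arms coded A and B until the analysis code is fixed.

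The cost is protocol wording, a short script, one extra data field and some assignment of roles. The blood-test visit already exists for both arms, so no new contact is needed. The downside is slightly less scheduling flexibility at 24 weeks.
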